4.9.2 Treatment Visits 1 to 18 -Visits 1-6

Regular treatment visits (1 to 18) occur on non-consecutive days, 3 times per week for 6 weeks.

Purpose: The purpose of the treatment visits is to administer NIR-TLT and collect data to assess the effect of each of the NIR-TLT dose effects on MDD symptomatology (antidepressant effect) and tolerability.

Procedures: Trained study personnel will deliver NIR-TLT to study participants. Treatment visits are estimated to last approximately 429 seconds (7.15 minutes) and will take place in a dedicated NIR-TLT (laser safety) office. Only the subject and the staff administering NIR-TLT will be present during the session. The subject will lie comfortably on an examination bed or sit in a recliner, a cervical pillow (U-shaped) may be used for comfort and to prevent the helmet connector cables from being stepped on, bent or damaged. The NIR-TLT application sites (left and right forehead) will be inspected for skin lesions (e.g., lacerations or signs of inflammation) that might contraindicate treatment. During treatment sessions, a warning sign will be hung on the office door. Ideally the place where treatment is administered should be at a temperature of 25°C +/- 2°C.

Prior to treatment with the EXPi device, the subject's forehead is cleaned with 70% isopropyl alcohol, the cap is placed on the subject's head and secured, and the treatment beam locations are adjusted to match the F3 and F4 EEG sites (or very close if the site is covered by hair), the eyebrows may be used as a reference for placement of the lower edge of the helmet. The operator and subject are provided with appropriate laser safety glasses (optical density rating > 5.0 at 808 nm). Disposable caps may be used for hair control if necessary.

Trained personnel administering NIR-TLT will make every effort to never shine light into or near the subject's eyes. Patients and staff will wear safety glasses selected for the biophysical properties of NIR-TLT in accordance with Occupational Safety and Health Administration (OSHA) guidelines. The patient may sleep during the time of therapy administration.

The NIR-TLT delivery is expected to last no longer than 7.15 minutes (429 seconds) in total (simultaneous application to the left and right forehead). The subject will be allowed to rest for 5 minutes after NIR-TLT delivery. The skin at the application sites will be inspected again after laser application. A log will be kept with the dates of delivery of the NIR-TLT.

Near Infrared Transcranial Laser Therapy in Subjects with Major Depressive Disorder: A study of Dosing with Laser.

treatment per study subject. The use of cell phones, tablets, computers or electronic devices will not be allowed during laser administration.

[figure not shown]
During treatment visits and prior to NIR-TLT, study personnel will collect tolerability (safety) and efficacy data:

1. Safety data: SAFTEE-SI (self-assessed), C-SSRS, adverse events and concomitant medication form.
2. Efficacy data - HAMD-17.

In addition to the evaluation described above, during visits 1, 9 and 18:

Prior to the NIR-TLT study, the staff will collect primary efficacy data from metric measurements and brain electrophysiology data:

1. Efficiency data:
 - a. Doctor-administered scales (1): HAMD-17, QIDS-C and CGI-S.
 - b. Patient-Reported Scales (1): ASQ and SDQ
2. Brain Electrophysiology Data - Study personnel will conduct a first 10-minute EEG recording session, treat the patient according to their NIR-TLT group randomization, and then conduct a second 10-minute EEG recording session as soon as possible after the end of treatment, but within 15 minutes.

3. Exploratory PET scan data: A PET scan will be performed on the participants selected to be part of the research subgroup, before the first treatment visit and within 24 hours of the end of the last intervention (visit 18).

4.9.3 Follow-up visit (Post Treatments) - Week 8

Near Infrared Transcranial Laser Therapy in Subjects with Major Depressive Disorder: A study of Dosing with Laser.

The next visit will occur two weeks after the last cerebral blood flow impact visit.

Purpose: The purpose of the follow-up visit is to evaluate the long-term antidepressant effect of NIR-TLT.

Procedures: During the follow-up study, staff will collect tolerability (safety) and efficacy data:

1. Safety data: SAFTEE-SI (self-assessed), adverse events and concomitant medication form.

2. Efficiency data:

- a. Doctor-administered scales (1): HAMD-17, QIDS-C and CGI.
- b. Patient-reported scales (1): SDQ and ASQ.

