4.1 Study Aims

Primary Aim:

A. To evaluate and compare the effect(s) of each of the four doses of NIR-TLT on depressive symptomatology: antidepressant effect, in patients with major depressive disorder (MDD).

Hypothesis 1: Total HAM-D 17 scale scores will vary in a NIR-TLT dose-dependent manner, with BPW dose being more effective.

We also expect to be able to estimate the effect size of the antidepressant action as a function of the irradiance applied to the NIR-TLT skin, with the BPW dose being more effective.

Secondary Aims:

B. Compare safety and tolerability at each dose of NIR-TLT.

Hypothesis 2: The doses of NIR-TLT tested in this study will be safe and well tolerated by patients with MDD, as assessed by SAFTEE-SI and reports of serious adverse events. We do not anticipate dose-dependent differences in reported side effects.

C. To compare the effect(s) of each of the four doses of NIR-TLT on brain electrophysiology.

Exploratory Aim:

D. To describe the findings visualized in PET, related to the brain metabolism of the participants, before and at the end of the intervention under study.

4.2 Rationale for the use of the EXPi device:

Transcranial photobiomodulation (t-PBM) with near infrared (NIR) laser therapy has emerged as a possible antidepressant treatment in both animal models (Mohammed et al.2016; Salehpour 2016-2017; Xu et al.2017; Wu et al.2012), and in human studies (Cassano 2015- 2017; Caldieraro et al.2018) t-PBM. NIR appears to increase brain metabolism (by activating the cytochrome C oxidase in the mitochondria), to increase neuroplasticity and to modulate the

Near Infrared Transcranial Laser Therapy in Subjects with Major Depressive Disorder: A study of Dosing with Laser.

endogenous opioids, while decreasing inflammation and oxidative stress. (Chung et. al. 2012; Yu et. al. 1997; Oron et al. 2007, Mochizuki et al. 2002) t-PBM penetrates deep into the cerebral cortex, modulates cortical excitability, and improves cerebral perfusion and oxygenation. The safety of t-PBM has been studied in a sample of 1410 acute stroke patients, with no significant difference in adverse event rates between t-PBM and sham exposure. (Hacke et al. 2014; Lamp et al. 2007, Zivin et al. 2009) Uncontrolled studies suggest an antidepressant effect of t-PBM in subjects suffering from MDD (Cassano 2015-2017; Caldieraro et al. 2018).

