4.3 Dosing Rationale

The laser dose to be used in the present clinical trial is derived from previous clinical experience with the use of other versions of the medical device in studies conducted in patients with acute stroke, major depressive disorder and Alzheimer's disease in whom lasers have been administered with this device, which has provided guidance on safe and potentially effective doses in the study population. A summary of this information is presented in Table 1.

Laser devices have a potential risk of retinal injury when used incorrectly; this is mitigated by the use of protective eye equipment "goggles" and proper procedures to ensure eye safety (Barkana & Belkin, 2000).

No serious adverse events were found in our literature review (Caldieraro & Cassano, 2019). Two open-label studies using 1 and 6 sessions of t-PBM reported no treatment emergent side effects (Cassano et al., 2015; Schiffer et al., 2009).

The safety of a t-PBM session was evaluated in three large RCTs with a combined sample of 1410 stroke subjects (Hacke et al., 2014; Huisa et al., 2013; Lampl et al., 2007). No significant differences in the rate of adverse effects were observed between the group receiving NIR laser (808 nm; 5W, 700 mW / cm²) or sham.

A clinical trial with 16 sessions of t-PBM reported a higher number of mild side effects in the active treatment group, the most frequent being insomnia, "seeing bright colors," "an ashtray taste," and irritable mood (Cassano et al., 2018, p. 2). Other potential risks are related to improper administration and will be mitigated by safety procedures, such as the use of protective eyewear.

The risk of thermal injury from PBM administered with the parameters used in the studies we reviewed is considered minimal and limited to the skin. In ten people treated by TBI with 10-15 W lasers, a much higher power than that used in t-PBM, skin temperature increased to no more than 30°C with rapid cooling after removal of the NIR light. Clinically, patients reported slight skin heating, but no discomfort (Morries et al., 2015).

Near Infrared Transcranial Laser Therapy in Subjects with Major Depressive Disorder: A study of Dosing with Laser.

TITLE	PUBLISHED					NOT PUBLISHED			PRESENT
	NEST	NEST-2	NEST-3	ELATED	ELATED-2	ELATED-3	TRIADE	TRAP-AD	"ELATED-4"

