5.5 Efficacy and Safety Analysis for the Aims

It will be carried out as follows:

A. Antidepressant effect of NIR-TLT doses:

To compare the antidepressant effects of NIR-TLT doses, mean changes in HAM-D 17 scores (for evaluation of the Primary Assessment Criteria) and QIDS-C and CGI-S (for evaluation of the Secondary Assessment Criteria), will be performed for each dose at 3 time points (visit 1, visit 9 and visit 18) will be compared using a repeated measures ANCOVA. A significant ANCOVA interaction in mean score changes between groups will be taken as indicating that the groups have different antidepressant efficacy. If significant ANCOVA interactions are found, paired samples t-tests will be used to explore differences between scores/groups.

Both the full analysis and the analysis by intention will be performed to analyze the severity of depression at the endpoint. Patient attrition and dropout will be analyzed. The possible

Transcranial Near Infrared Laser Therapy in Subjects with Major Depressive Disorder: A Laser Dosing Study.

differences between treatment groups in dropouts will be examined with Fisher's exact test.

B. Brain electrophysiological effect of NIR-TLT doses:

To compare the effects of NIR-TLT doses on brain electrophysiology, changes in EEG spectral power in all spectral bands for each dose at 3 time points (visit 1, visit 9, and visit 18) will be compared using a repeated measures ANCOVA. A significant ANCOVA interaction in mean score changes between groups will be taken as indicating that the groups have different effects. If significant ANCOVA interactions are found, paired samples t-tests will be used to explore differences between groups.

C. Safety and tolerability of NIR-TLT doses:

To compare the safety and tolerability of NIR-TLT doses, mean changes iSAFTEE-SI scores at 3 time points (visit 1, visit 9, and visit 18) will be compared using a repeated measures ANOVA. A significant ANOVA interaction in mean score changes between groups will be taken as indicating that the NIR-TLT doses have different tolerability. If significant ANOVA interactions are found, paired samples t-tests will be used to explore differences between groups.

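### Sleep is permitted at the EEG visits and the timing of the post-treatment EEG is loose, which adds avoidable noise to aim C and confounds within-arm pre/post EEG changes

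*Protocol*

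**What the plan says.** Aim C in section 4.1 is a comparison of arms: "To compare the effect(s) of each of the four doses of NIR-TLT on brain electrophysiology". Section 4.9.2 sets the conduct of the visits:

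- **Sleep.** "The patient may sleep during the time of therapy administration". This covers all 18 treatment visits.
- **First recording (visits 1, 9 and 18).** "Study personnel will conduct a first 10-minute EEG recording session" before treatment.
- **Second recording (same visits).** A "second 10-minute EEG recording session as soon as possible after the end of treatment, but within 15 minutes".
- **Rest.** "The subject will be allowed to rest for 5 minutes after NIR-TLT delivery".

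Section 5.5 B analyses "changes in EEG spectral power in all spectral bands for each dose at 3 time points" with a repeated measures ANCOVA. It judges the result on the group interaction and follows a significant interaction with paired-samples t-tests. The protocol does not ask sites to control or record sleep, or to record the delay to the second EEG.

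**The concern.** Section 5.5 B includes every spectral band, and spectral power changes with vigilance. The setting invites dozing: section 4.9.2 has the participant on a bed or in a recliner, with a neck pillow if wanted, in a room at about 25°C and without electronic devices. A participant who has just slept, or whose second EEG begins sooner than another's, can show a different pre-to-post change for reasons unrelated to the laser.

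Two things are at stake. One is precision in the comparison of arms. The other is the meaning of any pre/post change within one arm, where no sham contrast removes the effect of dozing. The arms are independent groups, so the paired tests in 5.5 B, although described as exploring differences between groups, could in practice be run as within-arm tests.

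**Working it through.** **What the plan fixes.** The protocol gives no sample size or power figure for EEG, so there is no plan figure to reproduce. From section 5.3: 28 per arm, 112 in total, with a 20% loss rate. That leaves 28 × 0.8 = 22.4, taken as 22 per arm. Planned post-treatment recordings number 3 × 112 = 336.

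**Timing.** Let t be the start of the second EEG, in minutes after treatment ends.
- If the 15-minute limit applies to the start, t can be anywhere from 0 to 15.
- If it applies to completion, t can be from 0 to 15 − 10 = 5.

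The wording allows both readings.

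**Noise model.** All inputs here are assumptions; the documents give none. A share p of participants doze, and dozing shifts the pre-to-post EEG change by s SD. Take p = 10% to 50% and s = 0.5 to 1.0. For one visit and two arms:
- variance inflation = 1 + p(1 − p)s²
- between-arm bias = (p in the active arm − p in the sham arm) × s
- within-arm mean shift = p × s

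Power uses an illustrative effect of 6.4 / 7.091 = 0.90 SD, borrowed from the HAM-D-17 figures in 5.3 because no EEG effect is stated. Tests are two-sided at 0.05 with 22 per arm. Error rates come from 20,000 simulated trials per row.

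**Equal dozing in all arms:**

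| p | s | Variance inflation | Between-arm type I error | Between-arm power | Within-arm false-positive rate |
|---|---|---|---|---|---|
| 0 | – | 1.00 | – | 83% | – |
| 0.1 | 0.5 | 1.02 | 5.2% | 82% | 5.5% |
| 0.1 | 1.0 | 1.09 | 4.9% | 80% | 6.8% |
| 0.3 | 0.5 | 1.05 | 5.0% | 81% | 10.5% |
| 0.3 | 1.0 | 1.21 | 5.2% | 76% | 22.7% |
| 0.5 | 0.5 | 1.06 | 5.0% | 81% | 19.1% |
| 0.5 | 1.0 | 1.25 | 5.1% | 74% | 51.4% |

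Example for the last row: 1 + 0.5 × 0.5 × 1.0² = 1.25, so the effect of 0.90 SD shrinks to 0.9026 / √1.25 = 0.81 SD. Simulated between-arm bias was about zero in every row.

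**Unequal dozing, purely as a what-if** (20% in sham; 10, 20 or 30 points more in an active arm): bias runs from 0.10 × 0.5 = 0.05 SD to 0.30 × 1.0 = 0.30 SD, and type I error from 5.4% to 14.4%.

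**Limits.** The model has one visit and two arms, whereas the plan has three visits and four arms. The within-arm rates are for a stand-alone test; in 5.5 B the paired tests follow only a significant interaction.

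**The case against.** The strongest reply is that randomization and sham already deal with this. Every arm has the same 429-second session, the same permission to sleep and the same EEG schedule, and 5.5 B judges the group interaction. This stands: equal dozing costs precision and does not bias the arm contrast.

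A reader might infer more from the text. Four such inferences are not supported:

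- **That active treatment makes dozing unequal.** Section 4.3 reports mild side effects in an earlier 16-session trial, "the most frequent being insomnia", and 4.20.1 lists disturbed sleep. Neither reports sleepiness in the chair, and after-effects of earlier sessions cannot operate at visit 1. If the laser itself causes drowsiness, the resulting EEG change is arguably part of the effect that aim C asks about. Equality is not assured either: 4.20.1 allows a sensation of warmth while 4.4.2 denies any perceptible difference, and sections 1 and 5.1 say the operator knows the assignment while 3.2 says the operator is blinded.
- **That the start of the second EEG varies by 15 minutes.** That is one reading; the other gives 5.
- **That acute and cumulative EEG change are mixed.** Section 5.5 B does not say which recording or contrast it means, but it does not pool the two, and a statistical analysis plan commonly settles this.
- **That recordings with sleep should be left out.** Sleep occurs after randomization, so leaving them out could create selection bias if treatment affects sleep.

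It may also be said that vigilance instructions belong in an EEG manual. That is possible for the recordings, but the sleep permission and the ambiguous time limit are in the protocol itself.

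**Conclusion.** The point holds as a cheap improvement in precision and interpretation for a secondary aim. Section 4.9.2 leaves vigilance uncontrolled at the visits where vigilance matters, and its time limit can be read in two ways. If dozing is equal across arms, the cost under the assumptions above is 2% to 25% more variance and a loss of about 1 to 9 percentage points of power for a 0.90 SD effect. A stand-alone within-arm pre/post test could then be positive without any laser effect in 5.5% to 51% of cases.

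The documents do not support the stronger conclusion that sleep confounds aim C. Bias in the arm contrast needs dozing that differs by arm, which the protocol neither shows nor rules out. The share who doze and the size of the EEG shift are unknown, so these figures illustrate scale and are not forecasts.

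**What to change.** In 4.9.2:

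1. Limit the sleep permission to visits other than 1, 9 and 18. At those three visits, keep participants awake through treatment and both recordings, by the same procedure in every arm.
2. Start the second EEG at one fixed interval after treatment, and say whether the 15-minute limit means start or finish. Starting after the existing 5-minute rest satisfies both readings (5 + 10 = 15), though with no slack if the limit means finish.
3. Record any sleep and the actual start time, for description only. Do not exclude recordings on that basis.

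In 5.5 B, base EEG conclusions on the contrast with sham and not on within-arm pre/post tests.

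The cost is a few sentences and two recorded items. The staff member giving treatment is already in the room. The downside is slightly less comfort at 3 of 18 visits. With the rest placed between treatment and the second EEG, these steps take 10 + 7.15 + 5 + 10 = 32.15 minutes, so the 30-minute session estimate in 4.4 should be adjusted for EEG visits.

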4.9.4 Completion

If, during the study, a subject's CGI-S increases more than 2 points or rises above a score of 5, or if they become actively suicidal according to the C-SSRS scale, the subject will be referred to their treating doctor and advised to start or switch to another FDA-approved antidepressant medication. Such subjects may or may not be terminated from the study, depending on the severity of symptoms, at the clinical judgment of the principal investigator. Subjects who are considered actively suicidal and in imminent danger will be terminated from the study and referred to the appropriate local MGH or NKI emergency room for evaluation and subsequent hospitalization, or, if the subject is appropriate for outpatient monitoring, will be referred to their treating doctor for frequent appointments and follow-up. Each subject will have the investigator's contact information, as well as instructions on how to call emergency services, if necessary. We will encourage subjects to continue enrollment in the study through follow-up visits, regardless of discontinuation of NIR-TLT.

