4.4 Study Design

This study is a multicenter, randomized, sham-controlled, double-blind study on the use of transcranial continuous light therapy as a treatment for depressive symptoms in patients with major depressive disorder (MDD). Laser light therapy is tested in a strict parallel design.

This study will include 112 subjects randomly assigned to each of the four NIR-TLT treatment groups (28 subjects/group).

All subjects will receive three NIR-TLT treatments per week for 6 weeks and will complete a follow-up evaluation two weeks after treatment completion. All subjects and investigators (except the study statistician) will be blinded to treatment sequence assignment.

Energy will be administered at a wavelength of 808 nm, bilaterally to two frontal areas on the left and right side of the forehead, at or near electroencephalography sites F3 and F4. To maintain blinding, the treatment duration will be 429 seconds (7.15 minutes) for all groups. The treatment exposure (time during which the laser is active for the duration of the treatment) will be specific for each group, controlled by the device to normalize the treatment fluence of each active session per treatment location. Treatment will follow these specifications: wavelength 830 nm; average irradiance 350 mW / cm²; average fluence of 65.8 J / cm² (according to the parameters used in the ELATED-2 study at MGH with the Omnilux New U device) being the total fluence delivered: 3.6 kJ (bilateral) or 1.8 kJ (unilateral), either on the subject's forehead, at or near electroencephalography (EEG) sites F3 and F4.

The entire session (which includes the 429-second treatment and all procedures described in the "Study Visits" section) is estimated to take 30 minutes or less (Schiffer et al., 2009) (Lampl et al., 2007, Zivin et al., 2009). Additional time is needed to prepare the subject, fit the necessary protections (e.g., goggles), inspect the subject's skin, set up the NIR-TLT devices, and give the subject time to rest after irradiation. NIR-TLT treatment will only be administered by trained personnel who are on study staff. All personnel administering the treatment must pass laser safety training created by the American Institute for Medical Laser Applications and approved by the relevant Committees. The duration of irradiation will be decreased if clinically indicated, based on tolerability as needed.

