4.17.2 Safety Monitoring

Study subjects will undergo frequent clinical assessments including depressive scores, concomitant medications, adverse events, and serious adverse events and unexpected device events will be recorded from study entry to completion. In addition, clinicians should monitor the safety of subjects by frequently asking them about their comfort during treatment delivery.

If skin erythema occurs, treatment will be discontinued. Patients will be instructed to contact the principal investigator of the study site or a member of his or her staff at any time between visits regarding adverse events or worsening of symptoms. If at any study visit, the subjects' clinical status significantly worsens from baseline (operationalized as the clinical global impression severity score, CGI-S, of 6 or greater) or if a subject develops active suicidal intent and/or plan, based on the C-SSRS scale and/or the clinical interview, the subject will be referred to the treating doctor to start an antidepressant medication or make appropriate changes in the treatment regimen. If the subject were considered to be in imminent danger as a result of suicidality, he/she would be discontinued from the study and referred to appropriate clinical treatment (see 4.9 Termination).

The two site principal investigators ([name], PI) will have bi-weekly conference calls (which will include all study staff); during these conference calls, they will discuss all adverse event reports to identify any safety concerns, based on such concerns, they may decide to temporarily discontinue study enrollment, modifications to the study protocol or terminate the study.

In addition, a Data and Safety Monitoring Board (DSMB), composed of at least 3 members not directly involved in the study, will review the SAEs annually. The research assistants responsible for data collection and storage will be aware of and comply with all regulatory requirements related to adverse events. In the event that a patient becomes ill or injured as a direct result of study participation, medical care will be provided. All adverse events (and device events) will be tracked to resolution and reported to the MGH or NKI IRB as serious in the event that:

Transcranial Near Infrared Laser Therapy in Subjects with Major Depressive Disorder: A Laser Dosing Study.

1. Not anticipated and possibly study-related (same report as SAE) or

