4.19 Subject Disposition Criteria

4.19.1 Withdrawal from the Study

Each subject and the investigator reserve the right at any time to terminate a subject's participation in the clinical investigation.

Possible reasons for withdrawal or removal from the study may include:

Transcranial Near Infrared Laser Therapy in Subjects with Major Depressive Disorder: A Laser Dosing Study.

1. The subject voluntarily withdraws consent.
2. The subject was ineligible according to the inclusion and exclusion criteria of the study.
3. The subject develops an adverse event that would not allow continuation in the study.
4. The subject has an adverse event that, in the opinion of the investigator, warrants withdrawal from the study. Pthera LLC must be notified within two business days.
5. The subject and/or the investigator make the decision that the subject should withdraw from the study.
6. Subject to death of participant.
7. Positive pregnancy test during eligibility procedures.
8. The subject misses one of the 3 scheduled sessions per week and it is not possible to make it up before the end of the week. When a subject withdraws or is withdrawn from the study, the following will be performed, if possible, at the study termination (exit) visit:
 - HAM-D-17
 - QIDS-C
 - CGI
 - C-SSRS
 - ADVERSE EVENT FORM
 - Concomitant Medication Form
 - ASQ (self-assessment)
 - SAFTEE-SI (self-assessment)
 - SDQ (self-assessment)

For all subjects who prematurely withdraw from the study, the date and reason for withdrawal will be documented.

4.19.2 *Loss of Follow-up*

If a center is unable to contact a subject or if the subject fails to appear for a visit, three documented telephone calls should be made, followed by a certified letter (or its equivalent, such as an e-mail). The certified letter should detail the need for the subject to appear for a visit, the center's failed attempts to contact the subject, and that failure to contact the center will cause the subject to be withdrawn from the study.

If the certified letter is returned to the center as undeliverable or the letter is delivered but the subject does not communicate with the center and no further contact is made with the subject or the subject's caregiver, then the subject will be considered lost to follow-up with the subject and suspended from the study. All attempts to contact the subject will be documented.

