6.4.1 Security Monitoring

Study subjects will undergo frequent clinical assessments including depressive scores, concomitant medications, adverse events, and serious adverse events, and unexpected device events will be recorded from study entry to completion. In addition, clinicians should monitor a subject's safety by frequently asking them about the subject's comfort during treatment delivery.

If skin erythema occurs, treatment will be discontinued. Patients will be instructed to contact the study site principal investigator or a member of his or her staff at any time between visits regarding adverse events or worsening symptoms. If at any study visit, the subjects' clinical status significantly worsens from baseline (operationalized as Clinical Global Impression Severity Score, CGI-S, of 6 or greater) or if a subject becomes actively suicidal with intent and/or plan, as per On the C-SSRS scale and/or clinical interview, the subject will be referred to the treating doctor to start an antidepressant medication or make appropriate changes in the treatment regimen. If the subject were considered to be in imminent danger as a result of suicidality, he/she would be discontinued from the study and referred to appropriate clinical treatment (see Section - 4.9 Termination).

The site will have bi-weekly conference calls with a designated Pthera LLC study monitor (which will include study RA's); During these conference calls, they will discuss all adverse event reports to identify any safety concerns, based on such concerns, they may decide to temporarily discontinue study enrollment, modifications to the study protocol or terminate the study.

In addition, a DSMB, consisting of at least 3 members not directly involved in the study and not employed by Pthera LLC, will review SAE quarterly. Research assistants responsible for data collection and storage will be aware of and comply with all regulatory requirements related to adverse events. In the event that a patient becomes ill or injured as a direct result of study participation, medical care will be provided. All adverse events (and device events) will be tracked to resolution and reported to the DSMB as serious in the event that they were not anticipated and possibly related to the study (same report as SAE) or meet any of the following criteria, any:

- (1) fatal event,
- (2) immediate life-threatening event,
- (3) event of permanent or substantial disability,

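### Participants terminated for imminent suicidal danger have no required contact up to week 8, so a new attempt or death after termination may go undetected

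*Protocol*

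**What the plan says.** Section 4.9.4 sets the rule: "Subjects who are considered actively suicidal and in imminent danger will be terminated from the study". These people go to an emergency room, or to their treating doctor if outpatient monitoring is suitable. Section 4.17.2 says that such a subject "he/she would be discontinued from the study and referred to appropriate clinical treatment", and section 6.4.1 says the same.

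For anyone who leaves early, section 4.19.1 provides one assessment: "When a subject withdraws or is withdrawn from the study, the following will be performed, if possible, at the study termination (exit) visit". The list includes the C-SSRS and the adverse event form.

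Several provisions soften the rule:

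- Section 4.9.4 ends with "We will encourage subjects to continue enrollment in the study through follow-up visits, regardless of discontinuation of NIR-TLT".
- Section 4.17.2 states "All adverse events (and device events) will be tracked to resolution", and section 6.4.1 has the same commitment, with reporting to the DSMB.
- Section 4.17.4 requires SAEs to be reported when they occur or come to light.
- Section 4.17.6 has withdrawals for adverse events telephoned to the sponsor, which may ask for more information.
- Section 4.18 keeps the investigator responsible for offering care options after termination.
- Section 4.19.2 prescribes repeated calls and then a letter when a subject misses a visit or cannot be reached.

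Section 4.17.5 says that reportable deaths include those during participation. Section 5.6 tabulates adverse events by arm to the end of the study.

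**The concern.** Elsewhere the protocol separates stopping treatment from leaving the study. Erythema stops treatment (4.17.2), and so does discomfort that persists to 24 hours (6.4). For imminent suicidal danger it ends participation instead. The participants at highest risk of the gravest outcome are therefore the ones for whom study observation may close earliest, while completers are observed to week 8.

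Worsening depression and suicidality are named risks in section 4.20.1, and comparing safety across doses is a stated aim. If a terminated participant makes a new attempt or dies before week 8 and the site does not hear of it, the event is absent from the by-arm safety tables (5.5 C and 5.6) and from the DSMB's SAE review. No later analysis can recover an event that was not collected, so this has to be settled in the protocol and the consent form and cannot be left to an analysis plan.

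**Working it through.** The protocol gives no figure to reproduce here. The check is to ask of each provision whether it would lead the study to detect a new attempt or death after termination and before week 8.

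| Provision | What it secures | Does it require a contact to week 8? |
|---|---|---|
| Exit visit (4.19.1) | One assessment around termination, where feasible | No |
| Tracking to resolution (4.17.2, 6.4.1) | Course of events already recorded | No; a new event is not covered |
| SAE reporting (4.17.4) | Report once the event is known | No; nobody is told to find out |
| Sponsor may request details (4.17.6) | Information on the withdrawal event | No |
| Care duties (4.9.4, 4.18) | Clinical care | No; no report back to the study is specified |
| Calls and letter (4.19.2) | Pursuit after a missed visit or failed contact | Not clearly; a terminated participant may have no visit left to miss |
| Encouragement (4.9.4) | Invitation to stay enrolled through follow-up | No; voluntary, and at odds with termination from the study |

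**Length of the gap.** The study summary gives 8 weeks of participation, and the table of assessments places V1 in week 1, V18 in week 6 and V19 in week 8. The weeks of termination are assumed.

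Weeks without a required contact = 8 − week of termination:

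- week 1: 8 − 1 = 7
- week 2: 8 − 2 = 6
- week 4: 8 − 4 = 4

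A stop at V18 would leave 8 − 6 = 2.

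**Number affected.** The protocol states no rate. Active ideation with intent and plan is excluded at entry, so few terminations are expected. An assumed 1 to 3 of 112 gives 1/112 = 0.9% to 3/112 = 2.7%.

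**What one missed event would do (illustration only).** With 28 per arm, take a table row for attempt or death. Exact (Clopper-Pearson) 95% intervals:

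- event captured: 1/28 = 3.6% (0.1% to 18.3%)
- event missed: 0/28 = 0% (0% to 12.3%)

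The intervals overlap widely. What is lost is an item in the description of harm, not a test result.

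**The case against.** The best reply is that the gap is narrow. A person in imminent danger is sent for emergency evaluation or close outpatient care. Hospitalisation makes the event an SAE under 4.17.1, it is tracked to resolution, and the sponsor is told at once. To be missed, an event must be new, follow the resolution of the first, fall within about 7 weeks and reach the investigator by no route. That is fair, and it limits the size of the point. It does not remove it, because each of those routes depends on someone happening to pass the news on.

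A second reply is that 4.19.2 does not exclude the exit visit or an encouraged week-8 visit, so the calls and letter might apply. They might, but that section deals with people who fail to appear or cannot be found. Its use for people whom the study itself has removed is unclear.

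Three stronger readings are tempting and are not supported:

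- **That the encouraged follow-up would fall before week 8 after an early stop.** Section 4.4 says that subjects "will complete a follow-up evaluation two weeks after treatment completion", but that sentence describes people who receive all six weeks of treatment. Section 4.9.3 says "The next visit will occur two weeks after the last cerebral blood flow impact visit", and this protocol defines no such visit. The heading of 4.9.3, the study summary and the table of assessments all put follow-up at week 8.
- **That deaths after termination are not reportable.** Section 4.17.5 says which deaths are included. It does not say that only those count, and 4.17.4 has no cut-off at termination.
- **That the suicidal crisis itself is lost, or that care lapses.** Section 6.4.1 states "All adverse events (and device events) will be tracked to resolution and reported to the DSMB as serious" when the listed criteria are met, and care is arranged.

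**Conclusion.** The point holds as a gap in required ascertainment. Participants terminated for imminent suicidal danger have one exit visit where feasible, a voluntary encouragement that conflicts with their termination, and no required contact that would detect a new attempt or death before week 8.

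Its impact is small. The length of the gap depends on the assumed week of termination, and the number affected is a guess, because the protocol gives no rate. The direction between arms is unknown. The triggering event is still counted, and a later SAE is still reported if it becomes known, so the right wording is that events may be missed. The change is worth making because it is cheap and protects safety data in the participants at highest risk.

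**What to change.** In 4.9.4, 4.17.2, 6.4.1 and 4.19.1, keep the stop of NIR-TLT and the referral as they are, but replace termination from the study with continued safety follow-up. Add one contact at the planned week-8 date, by telephone or through the treating doctor, unless the participant withdraws consent to contact. It should cover vital status, suicidal behaviour and SAEs. This also resolves the conflict with the closing sentence of 4.9.4.

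In 4.17.1 and 4.17.5, state that SAEs, suicidal behaviour and deaths are collected to that date and counted in the randomised arm.

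The cost is protocol and consent wording, including permission to approach the treating doctor, and a few extra contacts. It needs no extra staff or procedures. Making the same contact for every early loss would be a separate choice. At the planned 20% loss it would mean about 19 to 22 contacts (112 − 112/1.2 = 18.7 if the sample was inflated by 1.2; 112 × 0.20 = 22.4 if it was divided by 0.8). This point does not depend on it.
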